### **Funder**

[name] is supported by a fellowship from the European Society of Cardiology. Funding for monitoring patches will be provided from funds held by [name].

This protocol describes the POP-ECG-HF-AF study and provides information about procedures for entering participants. Every care was taken in its drafting, but corrections or amendments may be necessary. These will be circulated to investigators in the study. Problems relating to this study should be referred, in the first instance, to the Chief Investigator.

This study will adhere to the principles outlined in the NHS Research Governance Framework for Health and Social Care (2nd edition). It will be conducted in compliance with the protocol, the Data Protection Act and other regulatory requirements as appropriate.

## **GLOSSARY OF ABBREVIATIONS**

AE	ADVERSE EVENT
AF	ATRIAL FIBRILLATION
AR	ADVERSE REACTION
ASR	ANNUAL SAFETY REPORT
CI	CHIEF INVESTIGATOR
CRF	CASE REPORT FORM
DMC	DATA MONITORING COMMITTEE
ECG	ELECTROCARDIOGRAM
GAFREC	GOVERNANCE ARRANGEMENTS FOR NHS RESEARCH ETHICS
GCP	GOOD CLINICAL PRACTICE
GMP	GOOD MANUFACTURING PRACTICE
ICF	INFORMED CONSENT FORM
ISF	INVESTIGATOR SITE FILE
	MUST MALNUTRITION UNIVERSAL SCREENING TOOL
NHS R&D	NATIONAL HEALTH SERVICE RESEARCH & DEVELOPMENT
PI	PRINCIPAL INVESTIGATOR
PIS	PARTICIPANT INFORMATION SHEET
QA	QUALITY ASSURANCE
QC	QUALITY CONTROL
	RCT RANDOMISED CONTROL TRIAL
REC	RESEARCH ETHICS COMMITTEE
SAR	SERIOUS ADVERSE REACTION
SAE	SERIOUS ADVERSE EVENT
SDV	SOURCE DOCUMENT VERIFICATION
SSA	SPECIFIC ASSESSMENT SITE
TMG	TRIAL MANAGEMENT GROUP
TSC	TRIAL STEERING COMMITTEE

## **KEYWORDS**

Observational study, Heart failure, Atrial fibrillation, heart rate, ambulance ECG monitor,

## STUDY SUMMARY

**TITLE** A Prospective Observational Study of Prolonged Electrocardiographic Monitoring in Patients with Heart Failure in Sinus Rhythm or Atrial Fibrillation

**DESIGN** prospective observational study

**AIMS** Primary Objective: To quantify, in patients with heart failure who are either in sinus rhythm or in atrial fibrillation, the burden of brady- and tachy-arrhythmias and provide insights into the relationship between resting daytime heart rate and nocturnal heart rhythms

Secondary Objective: Identify the relationship between the burden of brady- and tachy-arrhythmias and clinical events

**OUTCOME MEASURES** Primary:

Co-primary endpoints

1. Identification of an arrhythmia for which there is a Class I or IIa recommendation for treatment with medication or devices

2. Either the above or one or more of the following (expanded endpoint) even if it does not otherwise meet guideline-indication for treatment:-

- Sinus bradycardia  $\leq 30$ bpm for  $\geq$ one minute
- High-degree atrioventricular (AV) block (3rd degree or Mobitz Type I or II)
- Pauses lasting  $\geq 3$  seconds (either sinus or AV block)
- Frequent ventricular ectopy defined as  $>1,000$  ectopic beats per day.
- Ventricular tachycardia with rate  $\geq 100$  bpm for  $\geq 5$  beats.

Secondary: Relationship of the above to all-cause mortality, cardiovascular mortality, hospitalization for heart failure or arrhythmia, implantation of a device with a capacity to pace the heart.

**POPULATION** Patients with Heart failure (HF)

**ELIGIBILITY**

1. Diagnosis of heart failure
2. Treated with loop diuretics for at least six weeks
3. Willing and legally able to sign informed consent
4. At least 18 years of age
5. New York Heart Association (NYHA) class II – IV

**DURATION** 5 years (clinical phase 18 months)

## 1. INTRODUCTION

### 1.1 BACKGROUND

Patients with heart failure may experience a variety of irregular heart rhythms (arrhythmia) that may or may not be symptomatic. Remarkably little-detailed information on arrhythmias in patients with heart failure has been published in the last decade, whilst methods of monitoring and the management of some types of heart failure has improved dramatically making older studies on this topic out-of-date. The emphasis in the 'old' literature was on fast heart rhythms, but there is growing awareness that slow heart rhythms might be even more important. Older technologies only assessed heart rhythm over 24-48 hours, but new, wearable, patient-friendly devices can monitor for much longer, creating a much richer patient arrhythmia profile.

We intend to conduct an observational study in patients with heart failure, investigating the incidence of arrhythmias using a wearable device that can monitor heart rhythm for up to 14 days. In addition to gathering routine clinical information, research assessments include a symptoms questionnaire and a corridor walk test. Patients will be followed for clinical events (interventions for arrhythmias, hospitalisation, death) for up to 5 years.

### 1.2 RATIONALE FOR CURRENT STUDY

The purpose of this study is to quantify the total arrhythmia burden (both slow and fast rhythms) in patients with heart failure using a wearable patch that can monitor the heart for up to 14 days. We then intend to follow the patients' progress over the next 5 years. We may find serious rhythm problems, in which case we will recommend treatment according to expert international guidelines (Guidelines on pacing 2013 and on sudden death 2015). This information will provide information on the incidence of severe arrhythmias that guidelines indicate should be treated and of the association of less severe arrhythmias (or their absence) with prognosis. This should improve patient care and inform the design of further research.

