### **3.1 STUDY OUTCOME MEASURES**

Primary:

Co-primary endpoints

1. Identification of an arrhythmia for which there is a Class I or IIa recommendation for treatment with medication or devices

2. Either the above or one or more of the following (expanded endpoint) even if it does not otherwise meet guideline-indication for treatment:-

- Sinus bradycardia  $\leq 30$ bpm for  $\geq$ one minute
- High-degree atrioventricular (AV) block (3rd degree or Mobitz Type I or II)
- Pauses lasting  $\geq 3$  seconds (either sinus or AV block)
- Frequent ventricular ectopy defined as  $> 1,000$  ectopic beats per day.
- Ventricular tachycardia with rate  $\geq 100$  bpm for  $\geq 5$  beats.

Secondary:

Relationship of the above to all-cause mortality, cardiovascular mortality, hospitalization for heart failure or arrhythmia, implantation of a device with a capacity to pace the heart.

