### Secondary endpoints

Relationship of the above to all-cause mortality, cardiovascular mortality, hospitalization for heart failure or arrhythmia, implantation of a device with a capacity to pace the heart.

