### Primary endpoint analysis

The primary analysis is the incidence rate of the primary composite endpoint.

We will investigate factors associated with the primary point. Pre-specified variables include: age, sex, NYHA class, body mass index, heart rate measured at examination, left ventricular ejection fraction, presence of calcific aortic or mitral valve disease, left atrial volume, conduction abnormalities on the 12-lead ECG, serum potassium and serum creatinine.

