### Secondary endpoint analysis

Secondary analyses include the incidence rate of each component of the primary composite endpoint and their association with the above variables.

Multi-variable models will be developed to investigate associations between the above variables, the components of the primary endpoint and all-cause mortality, cardiovascular mortality and the composite outcome measure.

Data and all appropriate documentation will be stored for a minimum of 10 years after the completion of the study, including the follow-up period.

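### The outcome analyses relate prognosis to two nested endpoints, and neither isolates the patients with only a less severe arrhythmia whose prognosis the rationale promises to report

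*Combined protocol and SAP*

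**What the plan says.** Section 1.2 (Rationale for current study) sets out two products of the study. One is the incidence of severe arrhythmias that guidelines say should be treated. The other is information "of the association of less severe arrhythmias (or their absence) with prognosis".

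Section 3.1 (Study outcome measures), repeated under Endpoints in section 7, defines two co-primary endpoints:

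- First: "Identification of an arrhythmia for which there is a Class I or IIa recommendation for treatment with medication or devices".
- Second: "Either the above or one or more of the following (expanded endpoint) even if it does not otherwise meet guideline-indication for treatment", followed by five listed arrhythmias.

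The secondary endpoint is then: "Relationship of the above to all-cause mortality, cardiovascular mortality, hospitalization for heart failure or arrhythmia", with implantation of a pacing-capable device as a further outcome.

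The Secondary endpoint analysis adds models: "Multi-variable models will be developed to investigate associations between the above variables, the components of the primary endpoint and all-cause mortality", together with cardiovascular mortality and a composite outcome. It does not say how the components are entered, whether the first co-primary endpoint is one of them, or what the reference group is. The Primary endpoint analysis reads: "The primary analysis is the incidence rate of the primary composite endpoint". It does not say which co-primary endpoint that is.

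**The concern.** The second endpoint contains the first by definition. Relating each of the two yes/no endpoints to outcome therefore gives two contrasts, and neither compares patients who have only a less severe arrhythmia with patients who have none.

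A raised risk among patients positive on the second endpoint could come wholly from the guideline-indicated patients inside it. Those patients may also be managed differently, because the Treatment procedure section says that abnormalities found will be treated according to guidelines. Device implantation is an outcome, while the first endpoint includes arrhythmias that carry a device recommendation. For that outcome in particular, an association of the second endpoint could say little about less severe arrhythmia.

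At stake is a result that section 1.2 names as improving care and informing further research. The primary estimates of how common the arrhythmias are do not depend on this.

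**Working it through.** **1. The plan's own figures.** The plan gives no figure for this contrast. Its precision statement reproduces: (1.960 + 1.282) × √(p(1−p)/200) gives 5.0%, 9.9% and 11.5% at p = 5%, 25% and 50%, against the stated approximate 5%, 10% and 12% (two-sided 0.05 assumed, 90% power as stated). The expected deaths, more than 50 in the first year among 400 patients, correspond to at least 50/400 = 12.5%. The point below concerns endpoint structure and does not rest on the precision figures.

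**2. Set logic.** Take three exclusive groups: (a) guideline-indicated, (b) expanded-list arrhythmia without a Class I or IIa indication, (c) neither.

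| Endpoint | Positive | Negative |
|---|---|---|
| First co-primary | a | b + c |
| Second co-primary | a + b | c |

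Groups (a) and (c) each fill a cell of their own. Group (b) never does.

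**3. Size, for illustration only.** The documents give neither the shares of the three groups nor their risks, so both are assumed. Let g, m and n be the shares of (a), (b) and (c), and let Ra and Rb be risk ratios against (c).

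- Second endpoint, positive versus negative: (g·Ra + m·Rb)/(g + m).
- First endpoint, positive versus negative: Ra ÷ [(m·Rb + n)/(m + n)].

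With Ra = 2.5:

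| g / m / n | Second, Rb = 1.0 | First, Rb = 1.0 | Second, Rb = 1.5 | First, Rb = 1.5 |
|---|---|---|---|---|
| 5 / 45 / 50% | 1.15 | 2.50 | 1.60 | 2.02 |
| 5 / 20 / 75% | 1.30 | 2.50 | 1.70 | 2.26 |
| 10 / 15 / 75% | 1.60 | 2.50 | 1.90 | 2.31 |
| 25 / 25 / 50% | 1.75 | 2.50 | 2.00 | 2.14 |

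Example, second row: (0.05 × 2.5 + 0.20 × 1.0)/0.25 = 0.325/0.25 = 1.30. Less severe arrhythmia has no effect here, yet the second endpoint appears associated with risk. The first-endpoint contrast stays at 2.50 when Rb = 1.0 and falls only when Rb exceeds 1.

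**4. Power of (b) versus (c).** Assume 50 deaths over both cohorts, two-sided 0.05, and a risk of 2.5 in group (a) relative to (c). Deaths falling in (b) and (c) are E = 50(m·HR + n)/(m·HR + n + 2.5g). Power is Φ(√(E·q(1−q))·ln HR − 1.96), with q = m/(m + n).

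For 5 / 20 / 75% and HR 1.5: E = 50 × 1.05/1.175 = 44.7, q = 0.20/0.95 = 0.211, power 20%.

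| g / m / n | HR 1.5 | HR 2.0 |
|---|---|---|
| 5 / 20 / 75% | 20% | 48% |
| 5 / 45 / 50% | 28% | 65% |
| 25 / 25 / 50% | 18% | 44% |

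**The case against.** **The component models may already do the job.** The second endpoint can be read as a composite in which the first is one component. If so, modelling "the components of the primary endpoint and all-cause mortality, cardiovascular mortality and the composite outcome measure" could adjust each listed arrhythmia for guideline status. This stands in part: a joint model could partly separate the groups. However, the plan does not say that the first endpoint enters or that the components are fitted jointly. Fitted singly, a component such as pauses can hold patients who meet a guideline indication and patients who do not.

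**The yardstick is one sentence of rationale.** The secondary objective (section 2.2) speaks only of arrhythmia burden and clinical events, and section 1.2 does not define less severe. Equating it with the expanded list is an interpretation, and group (c) still includes lesser findings such as ectopy at or below 1,000 beats per day. This is fair, but the expanded list is the only definition the plan offers for arrhythmias short of a guideline indication, and the rationale's promise is explicit.

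**The distortion may be lost in noise.** Suppose 20, 80 and 300 patients in (a), (b) and (c), with assumed one-year mortality of 30%, 12.5% and 12.5%. The second endpoint then gives (20 × 0.30 + 80 × 0.125)/100 = 16% against 12.5%, a ratio of 1.28. With 16/100 against 37.5/300 deaths, the standard error of the log ratio is √(1/16 − 1/100 + 1/37.5 − 1/300) = 0.275, so the 95% interval is about 0.75 to 2.20. That is correct for one year. It does not make the pooled contrast the right one, and follow-up to 5 years will add events.

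**Stronger readings that a reader might infer.** One is that neither the less severe group nor the group without arrhythmia is isolated. The documents do not support this: patients negative on the second endpoint are exactly those with neither. Another is that the first-endpoint contrast is necessarily diluted. In the example just given it is 0.30/0.125 = 2.4 whether or not the 80 patients sit in the reference group. A third is that the plan cannot produce the promised result. It could, through a joint model, but it does not commit to one.

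**Conclusion.** The point holds in limited form. The nesting and the absence of an expanded-list-only group follow from the plan's definitions and need no assumption. Because the secondary endpoint relates outcomes to these endpoints, an association for the second could arise from its guideline-indicated subset.

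The size is unknown. Under an assumed risk ratio of 2.5 for guideline-indicated arrhythmia and no effect of less severe arrhythmia, the apparent ratio is about 1.15 to 1.75, depending on assumed shares. Dilution of the first-endpoint contrast (from 2.5 to between 2.02 and 2.31) requires less severe arrhythmia itself to carry risk, here an assumed ratio of 1.5. The plan should be changed because the change costs little and lets the study answer a question it poses.

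**What to change.** In Secondary endpoints and Secondary endpoint analysis:

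1. Classify each monitored patient as (a) Class I or IIa arrhythmia, (b) expanded-list arrhythmia without such an indication, or (c) neither.
2. Pre-specify (b) versus (c) as the contrast for the outcome analyses, reported as an estimate with a confidence interval.
3. Report (a) versus (c) separately.
4. In the component models, enter first-endpoint status jointly with the listed components and state the reference group. Splitting all five components by guideline status would give sparse cells and is not needed.
5. State which endpoint the primary composite is.

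The cost is wording only, since the groups follow from cross-classifying two endpoints that the study already determines. There are two downsides. Group (a) may be small. Power for (b) versus (c) is low at about 50 deaths: roughly 18–28% at a hazard ratio of 1.5 and 44–65% at 2.0 under the assumed shares, with both cohorts combined. It improves as follow-up to 5 years adds events. The SAP should say so and present this contrast as estimation.

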## 2. STUDY OBJECTIVES

### 2.1 PRIMARY OBJECTIVE

To quantify, in patients with heart failure who are either in sinus rhythm or in atrial fibrillation, the burden of brady- and tachy-arrhythmias and provide insights into the relationship between resting daytime heart rate and nocturnal heart rhythms

### 2.2 SECONDARY OBJECTIVES

Identify the relationship between the burden of brady- and tachy-arrhythmias and clinical events.

## 3. STUDY DESIGN

Observational study; non-commercial.

Duration 5 years (clinical phase 18 months).

400 patients with heart failure

We will include patients with heart failure. We are investigating the prevalence of subclinical arrhythmias in this population and their association with clinical outcomes. The patient will have a 7-14 days ambulatory ECG after which we will follow them up every 6 months for up to 5 years. At each time point, we will contact patients by phone or post and ask them if they have any hospital admissions. Every effort will be made to ensure that we know the patients

mortality status, before each planned follow up. We will call the patient's GP prior to making any direct contact with the patients.

### **3.1 STUDY OUTCOME MEASURES**

Primary:

Co-primary endpoints

1. Identification of an arrhythmia for which there is a Class I or IIa recommendation for treatment with medication or devices

2. Either the above or one or more of the following (expanded endpoint) even if it does not otherwise meet guideline-indication for treatment:-

- Sinus bradycardia  $\leq 30$ bpm for  $\geq$ one minute
- High-degree atrioventricular (AV) block (3rd degree or Mobitz Type I or II)
- Pauses lasting  $\geq 3$  seconds (either sinus or AV block)
- Frequent ventricular ectopy defined as  $> 1,000$  ectopic beats per day.
- Ventricular tachycardia with rate  $\geq 100$  bpm for  $\geq 5$  beats.

Secondary:

Relationship of the above to all-cause mortality, cardiovascular mortality, hospitalization for heart failure or arrhythmia, implantation of a device with a capacity to pace the heart.

## **4. PARTICIPANT ENTRY**

### **4.1 PRE-REGISTRATION EVALUATIONS**

Review of the patients medical record for inclusion/exclusion criteria

### **4.2 INCLUSION CRITERIA**

1. Heart Failure
2. Treated with Loop Diuretics for at least six weeks
3. Willing and legally able to sign informed consent
4. At least 18 years of age
5. New York Heart Association (NYHA) class II - IV

### **4.3 EXCLUSION CRITERIA**

1. Myocardial infarction in the previous six weeks,
2. Implanted pacemaker, including cardiac resynchronisation device, or defibrillator
3. Already participating in an interventional randomized controlled trial assessing effects on morbidity and mortality (this study does not preclude participation in future clinical trials).

### **4.4 WITHDRAWAL CRITERIA**

No withdrawal criteria. Patients may decide to remove the monitoring patch, may request that their data are not analysed or that they are not followed up for clinical events. They may also decline any intervention advised based on the findings of the monitoring test. Patients with incomplete data for any reason will be replaced. All patients will be followed up unless they refuse. There are no stopping rules.

## **5. ADVERSE EVENTS**

### **5.1 DEFINITIONS**

**Adverse Event (AE):** any untoward medical occurrence in a patient or clinical study subject.

**Serious Adverse Event (SAE):** any untoward and unexpected medical occurrence or effect that:

- **Results in death**
- **Is life-threatening** – refers to an event in which the subject was at risk of death at the time of the event; it does not refer to an event which hypothetically might have caused death if it were more severe
- **Requires hospitalisation, or prolongation of existing inpatients' hospitalisation**
- **Results in persistent or significant disability or incapacity**
- **Is a congenital anomaly or birth defect**

Medical judgement should be exercised in deciding whether an AE is serious in other situations. Important AEs that are not immediately life-threatening or do not result in death or hospitalisation but may jeopardise the subject or may require intervention to prevent one of the other outcomes listed in the definition above, should also be considered serious.

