### **5.3 REPORTING PROCEDURES**

All adverse events should be reported. Depending on the nature of the event the reporting procedures below should be followed. Any questions concerning adverse event reporting should be directed to the Chief Investigator in the first instance.

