#### **5.3.1 Non serious AEs**

All such events, whether expected or not, should be recorded.

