#### **5.3.2 Serious AEs**

An SAE form should be completed and faxed to the Chief Investigator within 24 hours. However, relapse and death due to heart failure, and hospitalisations for elective treatment of a pre-existing condition do not need reporting as SAEs.

All SAEs should be reported to the London - Brent Research Ethics Committee where in the opinion of the Chief Investigator, the event was:

- 'related', ie resulted from the administration of any of the research procedures; and
- 'unexpected', ie an event that is not listed in the protocol as an expected occurrence

Reports of related and unexpected SAEs should be submitted within 15 days of the Chief Investigator becoming aware of the event, using the NRES SAE form for non-IMP studies. The Chief Investigator must also notify the Sponsor of all SAEs.

Local investigators should report any SAEs as required by their Local Research Ethics Committee, Sponsor and/or Research & Development Office.

Contact details for reporting SAEs  
email: [[contact]](mailto:[contact]) and [[contact]](mailto:[contact])  
Please send SAE forms to: [name]  
[contact] [name] (Mon to Fri 09.00 – 17.00)

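### The SAE definition includes unexpectedness, and the heart-failure exemption has no relatedness limit, so some serious events have no stated route to the Chief Investigator's causality judgement

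*Combined protocol and SAP*

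**What the plan says.** Section 5.1 gives two definitions. An adverse event is "any untoward medical occurrence in a patient or clinical study subject", with no condition on seriousness or expectedness. A serious adverse event is "any untoward and unexpected medical occurrence or effect that" leads to one of five listed outcomes, among them death, threat to life and hospital admission. A closing paragraph adds a discretionary route: "Medical judgement should be exercised in deciding whether an AE is serious in other situations".

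Section 5.3 opens with a general duty, "All adverse events should be reported", and then a routing rule: "Depending on the nature of the event the reporting procedures below should be followed". Two routes follow.

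- Section 5.3.1, for non-serious events: "All such events, whether expected or not, should be recorded".
- Section 5.3.2, for serious events: a form to the Chief Investigator within 24 hours and notification of the Sponsor. A report to the ethics committee within 15 days is added if the Chief Investigator considers the event both related to a research procedure and unexpected. Unexpected here means "an event that is not listed in the protocol as an expected occurrence".

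Section 5.3.2 also contains an exemption: "However, relapse and death due to heart failure, and hospitalisations for elective treatment of a pre-existing condition do not need reporting as SAEs".

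**The concern.** Seriousness and expectedness are normally separate steps. Seriousness decides whether an event goes quickly to the person who judges causality, and expectedness decides how far it travels after that. Section 5.1 merges the two. The site must decide whether a serious event is expected before it knows whether a form is due, and therefore before the Chief Investigator can consider relatedness.

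The exemption in 5.3.2 has a similar effect by another path. It is defined by the type of event alone and makes no exception for a suspected link to the patch or the walk test.

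What is at stake is the speed and completeness with which serious harm from a research procedure is recognised. The prevalence estimates and the sample size are not affected.

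**Working it through.** No arithmetic applies. The check is to follow different kinds of event through sections 5.1 and 5.3 as written.

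| Event | AE under 5.1? | SAE under 5.1, read literally? | Route |
|---|---|---|---|
| Non-serious, expected or not | Yes | No | 5.3.1: recorded |
| Serious, regarded by the site as unexpected, not exempt | Yes | Yes | 5.3.2: 24-hour form, Sponsor notification, relatedness judged |
| Serious, regarded by the site as expected, not exempt | Yes | No | Neither: the heading of 5.3.1 excludes it, and 5.3.2 is tied to SAE status |
| Heart-failure relapse needing admission soon after the walk test | Yes | Depends on expectedness | Exempt from SAE reporting either way |

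**Third row.** The general duty in 5.3 still applies, so the event must be reported. But 5.3 refers the reader to the procedures below it, and neither fits. What is missing is the route, the deadline, Sponsor notification and a defined relatedness judgement. The discretionary clause at the end of 5.1 does not fill the gap for the gravest events, because it addresses situations other than the listed outcomes of death, threat to life and hospitalisation.

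**Fourth row.** Section 6 lists the walk test and the patch as baseline assessments. The exemption does not ask whether either contributed, so the event need not reach the Chief Investigator as an SAE.

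**Internal consistency.** If 5.1 were meant literally, the later expectedness test in 5.3.2 would have almost nothing left to do, since every SAE would already be unexpected. The exemption for foreseeable heart-failure events would also be largely redundant. Section 5.3.1 states that expectedness is irrelevant for non-serious events, and no matching statement exists for serious ones. The sections therefore conflict.

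**How wide the gap is.** This depends on what *unexpected* means in 5.1, which does not define it.

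1. If the 5.3.2 meaning is carried back, an event is expected only if the protocol lists it. The protocol text contains no such list; the nearest thing is the exemption, which is not labelled as one. On this reading almost every event is unexpected, and the word in 5.1 excludes almost nothing.
2. If the site uses its own clinical judgement, the definition removes whatever the site considers foreseeable in NYHA class II to IV heart failure. A related event that is not listed as expected would then meet the 5.3.2 criteria for an ethics-committee report, yet need not reach the Chief Investigator on an SAE form.

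Nothing tells sites which meaning to use. The gap in the exemption exists under both.

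**The case against.** The strongest reply is that little is lost.

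- Section 5.3 requires every adverse event to be reported and directs questions to the Chief Investigator. This stands. A reader might infer that serious expected events go unreported or need not be recorded, and the documents do not support that.
- The only definition of *unexpected* is in 5.3.2 and, with no list, it excludes almost nothing. This is a fair account of what the authors probably intended. It is not an instruction to sites, and it does not touch the exemption.
- Ethics-committee reporting already excludes expected events. This is true when both sections use the word in the same sense. It fails when a site's own view of what is expected is wider than the absent list.
- Deaths and hospitalisations are captured separately, by six-monthly contact and electronic records (Subsequent Assessments), and mode of death is investigated (section 7). This stands for outcome capture. Neither source includes a relatedness judgement, and neither is designed to find a life-threatening or disabling event that led to no admission.
- The study has no protocol-driven treatment, its procedures are light, and no analysis of related SAEs is planned. This lowers the stakes. It also means that a charge of misreading a low related-SAE count would attack an inference the plan never makes.

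**Conclusion.** The point holds as a contradiction between sections 5.1 and 5.3.2, together with an exemption that lacks a relatedness limit. It merits correction because the rules bear on patient safety and the correction is nearly free. It is not evidence that events are being lost.

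Its size cannot be given as a count. A reader might take the more than 50 first-year deaths anticipated in section 7 as the measure. They are not: heart-failure deaths are exempt whatever 5.1 says, the documents do not say how many other deaths to expect, and deaths are identified by other means. A reader might also extend the point to arrhythmias found by the patch, using the prevalence scenarios in the sample-size section. That does not follow. Whether such an arrhythmia is serious turns on the discretionary clause in 5.1, which does not mention expectedness, and the scenarios are illustrative inputs for precision.

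The conclusion about the definition assumes that at least some sites read 5.1 literally and apply their own view of what is expected. The conclusion about the exemption needs only its plain wording.

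**What to change.** Reconcile sections 5.1 and 5.3 with two edits.

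1. Delete *and unexpected* from the SAE definition in 5.1. Every event with a listed serious outcome then enters 5.3.2, and expectedness is applied only by the Chief Investigator at the ethics-committee step.
2. Limit the 5.3.2 exemption for heart-failure relapse or death and elective admissions to events not suspected to be related to a research procedure, naming the patch and the walk test.

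The cost is a protocol wording amendment and a few more SAE forms. Design, sample size and analysis are unchanged.
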